6.5.7.2. CPT Score

Child-Pugh-Turcotte score should be assessed at all visits per [Table 6-1](#).

Table 6-1. Child-Pugh-Turcotte Classification of the severity of cirrhosis

	1	2	3
Hepatic Encephalopathy	None No encephalopathy and not on any treatment for hepatic encephalopathy	Medication-Controlled Subject is lethargic, may have moderate confusion Subject is receiving medical therapy for HE	Medication-Refractory Marked confusion/incoherent, rousable but sleeping unless aroused or comatosed
Ascites	None No ascites and not on treatment for ascites	Mild/Moderate Cross sectional imaging showing ascites Abdominal distension Medication for ascites	Severe (diuretic-refractory) Visible clinically
Bilirubin (mg/dL)	< 2	2-3	> 3
Albumin (g/dL)	> 3.5	2.8-3.5	< 2.8
INR	< 1.7	1.7-2.3	> 2.3

CPT score is obtained by adding the score for each parameter.

CPT class: A = 5-6 points
 B = 7-9 points
 C = 10-15 points

Records of concomitant medications for ascites and hepatic encephalopathy will be collected in the CRF.

6.5.8. Creatinine Clearance

Creatinine clearance is calculated by the Cockcroft-Gault equation {[Cockcroft et al 1976](#)}.

Male:
$$CL_{Cr} \text{ (mL/min)} = \frac{[140 - \text{age (years)}] \times \text{BW(kg)}}{72 \times S_{Cr}}$$

Female:
$$CL_{Cr} \text{ (mL/min)} = \frac{[140 - \text{age (years)}] \times \text{BW(kg)} \times 0.85}{72 \times S_{Cr}}$$

S_{Cr} = serum creatinine (mg/dL)

Actual body weight will be used for the CL_{Cr} .

6.5.9. 12-Lead ECG

Subjects will be required to rest in a supine position for ≥ 5 minutes prior to making a recording.

The investigator (or qualified designee) should review the ECG traces recorded in real time for clinically significant abnormalities. On treatment ECGs should be compared to the subject's Day 1 as part of routine safety monitoring.

6.5.10. Viral Sequencing (Archive)

Plasma samples will be collected at Day 1 and each subsequent visit for viral sequence analysis. At any unscheduled visit initiated for the purpose of confirming HCV virologic breakthrough, HCV viral sequencing/phenotype plasma sample must also be collected. Unused samples may be archived.

6.5.11. Single Pharmacokinetic (PK) Sample

Single PK blood samples will be collected for all subjects at each on-treatment visit and archived for PK analysis of SOF (and metabolites) VEL and RBV.

6.5.12. HBV DNA Sample

A sample for HBV DNA testing will be collected at on-treatment visits at Day 1 and at Weeks 4, 8, and 12 or Early Termination and all posttreatment visits. HBV DNA will only be tested in subjects who are HBcAb+ at Screening to monitor for HBV re-activation.

6.5.13. IL28B Testing

A blood sample will be obtained at Screening for specific genetic analysis of the rs12979860 (IL28B) genetic variant.

6.5.14. Archive Plasma Sample

PPD

[Redacted]

[Redacted]

[Redacted]

PPD

[Redacted]

[Redacted]

6.5.16. Pregnancy Testing

Female subjects of childbearing potential should be provided with Urine Pregnancy test kits, instructed on their use, and requested to continue to self-monitor for pregnancy between scheduled study visits, every 4 weeks, for 6 months after their last dose of RBV. If required by regulations, additional pregnancy tests beyond 6 months may be added. The subject will be contacted every 4 weeks and asked to report results of the urine pregnancy tests. If a positive urine pregnancy test is reported, the subject will be asked to return to the clinic for a confirmatory serum pregnancy test.

6.5.17. Health Related Quality of Life Survey

A health related quality of life survey, SF-36, CLDQ-HCV, FACIT-F, and WPAI, will be completed by patients at Day 1, Week 12 and posttreatment Week 12, and Early Termination (if appropriate). The subject should read the questionnaire by himself/herself and write/mark answers directly onto the questionnaire.

7. ADVERSE EVENTS AND TOXICITY MANAGEMENT

7.1. Definitions of Adverse Events, Adverse Reactions, and Serious Adverse Events

7.1.1. Adverse Events

An adverse event (AE) is any untoward medical occurrence in a clinical study subject administered a medicinal product, which does not necessarily have a causal relationship with the treatment. An AE can therefore be any unfavorable and/or unintended sign, symptom, or disease temporally associated with the use of a medicinal product, whether or not considered related to the medicinal product. AEs may also include pre- or posttreatment complications that occur as a result of protocol specified procedures, overdose, drug abuse/misuse reports, or occupational exposure. Preexisting events that increase in severity or change in nature during or as a consequence of participation in the clinical study will also be considered AEs.

An AE does not include the following:

- Medical or surgical procedures such as surgery, endoscopy, tooth extraction, and transfusion. The condition that led to the procedure may be an adverse event and must be reported
- Pre-existing diseases, conditions, or laboratory abnormalities present or detected before the screening visit that do not worsen
- Situations where an untoward medical occurrence has not occurred (eg, hospitalization for elective surgery, social and/or convenience admissions)
- Overdose without clinical sequelae (see Section 7.6.1)
- Any medical condition or clinically significant laboratory abnormality with an onset date before the consent form is signed and not related to a protocol-associated procedure is not an AE. It is considered to be pre-existing and should be documented on the medical history CRF.

7.1.2. Serious Adverse Events

A **serious adverse event** (SAE) is defined as an event that, at any dose, results in the following:

- Death
- Life-threatening (Note: The term “life-threatening” in the definition of “serious” refers to an event in which the subject was at risk of death at the time of the event; it does not refer to an event that hypothetically might have caused death if it were more severe)
- In-patient hospitalization or prolongation of existing hospitalization
- Persistent or significant disability/incapacity

- A congenital anomaly/birth defect
- A medically important event or reaction: such events may not be immediately life-threatening or result in death or hospitalization but may jeopardize the subject or may require intervention to prevent one of the other outcomes constituting SAEs. Medical and scientific judgment must be exercised to determine whether such an event is a reportable under expedited reporting rules. Examples of medically important events include intensive treatment in an emergency room or at home for allergic bronchospasm; blood dyscrasias or convulsions that do not result in hospitalization; and development of drug dependency or drug abuse. For the avoidance of doubt, infections resulting from contaminated medicinal product will be considered a medically important event and subject to expedited reporting requirements.

7.1.3. Clinical Laboratory Abnormalities and Other Abnormal Assessments as Adverse Events or Serious Adverse Events

Laboratory abnormalities without clinical significance are not recorded as AEs or SAEs. However, laboratory abnormalities (eg, clinical chemistry, hematology, and urinalysis) that require medical or surgical intervention or lead to study drug interruption, modification, or discontinuation must be recorded as an AE, as well as an SAE, if applicable. In addition, laboratory or other abnormal assessments (eg, electrocardiogram, x-rays, vital signs) that are associated with signs and/or symptoms must be recorded as an AE or SAE if they meet the definition of an AE or SAE as described in Sections 7.1.1 and 7.1.2. If the laboratory abnormality is part of a syndrome, record the syndrome or diagnosis (eg, anemia), not the laboratory result (ie, decreased hemoglobin).

For specific information on handling of clinical laboratory abnormalities in this study, please refer to Section 7.5

7.2. Assessment of Adverse Events and Serious Adverse Events

The investigator or qualified sub-investigator is responsible for assessing AEs and SAEs for causality and severity, and for final review and confirmation of accuracy of event information and assessments.

7.2.1. Assessment of Causality for Study Drugs and Procedures

The investigator or qualified subinvestigator is responsible for assessing the relationship to study drug therapy using clinical judgment and the following considerations:

- **No:** Evidence exists that the adverse event has an etiology other than the study drug. For SAEs, an alternative causality must be provided (eg, pre-existing condition, underlying disease, intercurrent illness, or concomitant medication).
- **Yes:** There is reasonable possibility that the event may have been caused by the investigational medicinal product.

It should be emphasized that ineffective treatment should not be considered as causally related in the context of adverse event reporting.

The relationship to study procedures (eg, invasive procedures such as venipuncture or biopsy) should be assessed using the following considerations:

- **No:** Evidence exists that the adverse event has an etiology other than the study procedure
- **Yes:** The adverse event occurred as a result of protocol procedures (eg, venipuncture)

7.2.2. Assessment of Severity

The severity grading of AEs will be assessed as Grade 1, 2, 3, or 4 using the GSI Grading Scale for Severity of Adverse Events and Laboratory Abnormalities ([Appendix 3](#)). For AEs associated with laboratory abnormalities, the event should be graded on the basis of the clinical severity in the context of the underlying conditions; this may or may not be in agreement with the grading of the laboratory abnormality.

7.3. Investigator Requirements and Instructions for Reporting Adverse Events and Serious Adverse Events to Gilead

Requirements for collection prior to study drug initiation:

After informed consent, but prior to initiation of study drug, the following types of events should be reported on the case report form (CRF/eCRF): all SAEs, regardless of cause or relationship, and adverse events related to protocol-mandated procedures.

7.3.1. Adverse Events

Following initiation of study drug, collect all AEs, regardless of cause or relationship, until 30 days after last administration of study drug and report to the CRF/eCRF database as instructed.

All AEs should be followed up until resolution or until the adverse event is stable, if possible. Gilead Sciences may request that certain AEs be followed beyond the protocol defined follow up period.

7.3.2. Serious Adverse Events

All SAEs, regardless of cause or relationship, that occur after the subject first consents to participate in the study (ie, signing the informed consent) and throughout the duration of the study, including the protocol-required posttreatment follow-up period, must be reported to the CRF/eCRF database and Gilead Drug Safety and Public Health (DSPH) as instructed. This also includes any SAEs resulting from protocol-associated procedures performed after informed consent is signed.

Investigators are not obligated to actively seek SAEs after the protocol defined follow up period; however, if the investigator learns of any SAEs that occur after study participation has concluded and the event is deemed relevant to the use of study drug, he/she should promptly document and report the event to Gilead DSPH.

- All AEs and SAEs will be recorded in the eCRF database within the timelines outlined in the eCRF completion guideline.

Electronic Serious Adverse Event (eSAE) Reporting Process

- Site personnel record all SAE data in the eCRF database and from there transmit the SAE information to Gilead DSPH within 24 hours of the investigator's knowledge of the event. Detailed instructions can be found in the eCRF completion guidelines.
- If for any reason it is not possible to record the SAE information electronically (ie, the eCRF database is not functioning) record the SAE on the paper serious adverse event reporting form and submit within 24 hours to:

Gilead Sciences, DSPH:

Fax: PPD

E-mail: PPD

- As soon as it is possible to do so, any SAE reported via paper must be transcribed into the eCRF Database according to instructions in the eCRF completion guidelines.
- If an SAE has been reported via a paper form because the eCRF database has been locked, no further action is necessary.
- For fatal or life-threatening events, copies of hospital case reports, autopsy reports, and other documents are also to be submitted by e-mail or fax when requested and applicable. Transmission of such documents should occur without personal subject identification, maintaining the traceability of a document to the subject identifiers.
- Additional information may be requested to ensure the timely completion of accurate safety reports.
- Any medications necessary for treatment of the SAE must be recorded onto the concomitant medication section of the subject's CRF/eCRF and the event description section of the SAE form.

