6.3. Posttreatment Assessments

6.3.1. 4-Week Posttreatment Visit (\pm 5 days)

- Assess presence and severity of ascites and hepatic encephalopathy for CPT score
- Vital signs
- Body Weight
- Assessment of AEs and concomitant medications
- Pregnancy prevention counseling
- Obtain blood samples for:
 - Hematology
 - Chemistry
 - Coagulation
 - HCV RNA
 - Viral sequencing
 - HBV DNA (only in subjects who are HBcAb+ at Screening)
- Obtain urine sample for:
 - Urine pregnancy test for females of childbearing potential only

6.3.2. 12 & 24 Week Posttreatment Visit (\pm 5 days)

- Assess presence and severity of ascites and hepatic encephalopathy for CPT score
- Vital signs
- Body Weight
- Perform symptom-directed physical examination
- Pregnancy prevention counseling
- Subject completes Health Related Quality of Life Questionnaire: SF-36, CLDQ-HCV, FACIT-F, and WPAI at posttreatment Week 12 only

- Obtain blood samples for:
 - Hematology
 - Chemistry
 - Coagulation
 - HCV RNA
 - Viral sequencing
 - HBV DNA (only in subjects who are HBcAb+ at Screening)
- Obtain urine sample for:
 - Urine pregnancy test for females of childbearing potential only

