8.1.2. Primary Endpoint

The primary efficacy endpoint is SVR12 (HCV RNA < LLOQ 12 weeks after cessation of study treatment regimen) in the Full Analysis Set (FAS).

The primary safety endpoint is any AE that led to permanent discontinuation of study drug.

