Appendix 2. Study Procedures Table

	Screen	Day 1 ^a	On-treatment Study Week (\pm 3 days)				Posttreatment Study Week (\pm 5 days)		
			2	4	8	12/ET	4	12	24
Informed Consent	X								
Determine Eligibility	X	X							
Medical History	X								
Physical Examination	X	X				X		X	X
Assess ascites and hepatic encephalopathy	X	X	X	X	X	X	X	X	X
Height	X								
Weight	X	X	X	X	X	X	X	X	X
Vital Signs ^b	X	X	X	X	X	X	X	X	X
12-Lead ECG	X	X							
AEs	X	X	X	X	X	X	X		
Concomitant Medications	X	X	X	X	X	X	X		
Pregnancy Prevention Counseling	X	X		X	X	X	X	X	X
Health Related Quality of Life ^c		X				X		X	
Study Drug Dispensing ^d		X		X	X				
Review of Study Drug Compliance ^e			X	X	X	X			
Hematology, Chemistry	X	X	X	X	X	X	X	X	X
Coagulation Tests	X	X	X	X	X	X	X	X	X
Urinalysis	X	X				X			

	Screen	Day 1 ^a	On-treatment Study Week (± 3 days)				Posttreatment Study Week (± 5 days)		
			2	4	8	12/ET	4	12	24
HCV RNA	X	X	X	X	X	X	X	X	X
HBV DNA ^f		X		X	X	X	X	X	X
Viral Sequencing		X	X	X	X	X	X	X	X
Single PK			X	X	X	X			
Serum β-hCG or Urine Pregnancy Test ^e	X	X		X	X	X	X	X	X
Urine Drug Screen	X								
HbA1c	X								
HCV & IL28B Genotyping	X								
HCV, HIV, HBV Serology	X								
Fibrotest [®]	X								

PPD

- a Day 1 assessments must be performed prior to dosing.
- b Vital signs include resting blood pressure, pulse, respiratory rate and temperature.
- c There are four Health Related Quality of Life surveys to provide to subjects: SF-36, CLDQ-HCV, FACIT-F, and WPAI.
- d The IWRS will provide direction on the specifics of each subject's study drug dispensing.
- e Instruct the subject to bring back all study drugs and study drug containers (used/unused).
- f Only for subjects who are HBcAb+ at Screening

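### SAEs must be reported through posttreatment follow-up, but no AE or SAE check is scheduled after posttreatment Week 4, and the specified SAE and death summaries stop at last dose plus 30 days

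*Protocol*

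**What the plan says.** **Reporting duty.** Section 7.3.2 covers every SAE, whatever its cause, from consent onward; events "throughout the duration of the study, including the protocol-required posttreatment follow-up period, must be reported to the CRF/eCRF database". The same section says that "Investigators are not obligated to actively seek SAEs after the protocol defined follow up period", so active seeking is expected until then. Sites are to "transmit the SAE information to Gilead DSPH within 24 hours" of the investigator learning of the event. For AEs in general, Section 7.3.1 sets a shorter window, "until 30 days after last administration of study drug".

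**Synopsis.** It names AEs among the posttreatment assessments without limiting them to a visit, and says under the safety criteria that AEs are collected for the whole study.

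**Visit schedule.** Section 6.3.1 lists an AE assessment at posttreatment Week 4. The list in Section 6.3.2, "12 & 24 Week Posttreatment Visit", has none. It does include ascites and encephalopathy assessment, laboratory samples and the item "Perform symptom-directed physical examination". In "Appendix 2. Study Procedures Table" the AE row also ends at posttreatment Week 4.

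**Summaries.** Sections 8.2.1.2 and 8.5 define the summarised safety data as first dose to last dose plus 30 days. Section 8.5.2 applies that limit to treatment-emergent AEs and places the lines for all SAEs and for deaths under those summaries. It sends all collected AEs to the data listings.

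**Primary safety endpoint.** Section 8.1.2: "The primary safety endpoint is any AE that led to permanent discontinuation of study drug".

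**The concern.** The protocol sets a long duty for SAEs but gives it neither a scheduled prompt nor a count after the first month off treatment. The AE row of Appendix 2 fits the 30-day AE window of Section 7.3.1. It does not fit the SAE window of Section 7.3.2 or the synopsis, which both run through follow-up.

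Safety and tolerability is a primary objective, the population has CPT C cirrhosis and there is no control arm. Readers will want to know how many subjects died or had an SAE while under observation. As specified, the summaries answer that only up to day 30 after the last dose, whereas the primary efficacy endpoint is read at posttreatment Week 12. The efficacy and safety tables can therefore disagree about the same subject.

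**Working it through.** 1. **Inputs.** Posttreatment period of 24 weeks (Section 3.3). Posttreatment visits at Weeks 4, 12 and 24, each ± 5 days (Section 6.3, Appendix 2). Week 24 only for subjects with SVR12 (Section 3.2). Summary cutoff at last dose + 30 days (Sections 8.2.1.2, 8.5, 8.5.2). About 50 subjects (Section 8.7).

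2. **The plan's own figure.** 4 + 12 + 24 = 40 weeks, or 6 + 12 + 24 = 42 weeks with extended screening. This matches Section 3.3, so the 24-week follow-up is read correctly.

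3. **Visit days after last dose.** Week 4 = 28 (23 to 33); Week 12 = 84 (79 to 89); Week 24 = 168 (163 to 173).

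4. **Time outside the summaries** = visit day − 30.
   - To Week 12: 84 − 30 = 54 of 84 days (64%); with the window, 79 − 30 = 49 to 89 − 30 = 59.
   - To Week 24, SVR12 subjects: 168 − 30 = 138 of 168 days (82%); with the window, 163 − 30 = 133 to 173 − 30 = 143.

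5. **Time after the last scheduled AE check.**
   - Week 4 to Week 12: 84 − 28 = 56 days; range 79 − 33 = 46 to 89 − 23 = 66.
   - Week 4 to Week 24: 168 − 28 = 140 days.

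6. **Efficacy and safety side by side.** Take a subject who has HCV RNA below LLOQ at posttreatment Week 4, has a fatal event starting on day 50, and dies before the Week 12 sample.
   - Section 8.2.2: the Week 12 value is missing, no later value can bracket it, so the subject is an SVR12 failure.
   - Section 8.5.2: onset is later than 30 days after stopping drug, so the event is not treatment-emergent. The other limb of the definition, AEs that led to premature discontinuation, does not bring in an event that begins after treatment has ended.
   - Result: counted against efficacy, absent from the death summary, present in the listing.
   - Limit: events are summarised by onset date, so a death after day 30 from an event that began by day 30 could still be counted. The mismatch is clear where onset also falls after day 30.

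7. **Weight of one subject.** 1/50 = 2.0 percentage points for each subject whose only SAE or death is late. The steps above give calendar time; the protocol provides no event rate from which to derive a number of affected subjects.

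**The case against.** The strongest reply is that nothing here is lost. The AE row ends where Section 7.3.1 ends AE collection. SAE reporting is event-driven and needs no visit-table entry. Weeks 12 and 24 are visits with a symptom-directed examination, CPT items and laboratory tests, at which a hospitalisation is likely to come up, and Section 9.1.5 requires source records to give the reason for early discontinuation. The tabulation half may be settled in the SAP, which is not shown; Section 8.5 sets what will be summarised and does not bar more. With about 50 subjects, late events can be counted from a listing.

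Much of this stands. The reporting duty is intact and late events are listed. But the 24-hour clock starts with the investigator's knowledge, which a scheduled question supports, and a subject who has died does not attend. The visit schedule is protocol content and is at odds with the synopsis. The 30-day limit, and the placing of SAEs and deaths under it, are written in the protocol itself.

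Three stronger readings should be resisted:
- A reader might infer that late SAEs go unreported. Section 7.3.2 says the opposite.
- A reader might infer that the primary safety endpoint is compromised. It concerns AEs that led to permanent discontinuation of study drug, so events starting after treatment do not enter it.
- A reader might infer that the tables would show few or no SAEs where many occurred. That would require assuming no earlier events in a CPT C population, and the protocol does not support such an assumption.

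**Conclusion.** The point holds as a limited inconsistency. Section 7.3.2 and the synopsis run through follow-up, while Section 6.3.2 and Appendix 2 schedule no AE or SAE check after posttreatment Week 4. The specified SAE and death summaries leave out nominally 54 of 84 posttreatment days, or 138 of 168 for SVR12 subjects. A late death can count as an SVR12 failure without appearing in the death summary.

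This rests on the protocol text alone, on nominal visit days, and on the SAP not adding a longer summary. The number of events affected is unknown. Severity is minor to moderate: ascertainment and presentation are weakened, but no stated estimate or endpoint is wrong.

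**What to change.** 1. In Section 6.3.2 and Appendix 2, add an SAE and survival-status item at posttreatment Weeks 12 and 24. Reconcile the synopsis wording on AE collection with Sections 7.3.1 and 7.3.2.

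2. In Section 8.5.2, keep the treatment-emergent tables. Add one summary of all deaths and SAEs from first dose through posttreatment Week 12, the last visit scheduled for all subjects (Section 3.4.1 keeps it for early terminators). Show later events separately. Give the number of subjects still followed for both parts: subjects may withdraw before Week 12, and only SVR12 subjects attend Week 24.

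3. Reconcile this summary with Section 7.6.2.2. The transplant exemption is worded for procedures within the 30-day AE window, whereas the new summary extends beyond it. State how transplant-related events and deaths are counted before and after day 30.

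**Cost.** Two schedule entries at existing visits, one table in two parts, and a few sentences of wording. The downside is that counts may look less favourable and will include events of the underlying disease, which an uncontrolled study cannot separate from treatment.
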